
ANNEX 5. CODES TO IDENTIFY THE OUTCOME VARIABLES

The codes will be updated for the data applications.

No.	Variable	ICD-10 / ICD-O-3 codes	READ codes	Outcome / Censoring variable	Analyses ¹
1	Urinary Tract cancer (malignant and carcinoma in situ)	C64-C68 D09.0, D09.1	Byu9, B837, B83z, B4A, B49	Outcome	D, P, S, F, NCC, MSM Sens
2	Bladder cancer (malignant and carcinoma in situ)	C67, D09.0	B49, B837, selected BB4 codes	Outcome	D, P, S, F, Sens
3	Renal cancer (malignant)	C64, C65	B4A0, B4A1	Outcome	D, P, S, F, Sens
4	Other urinary tract cancer (non-renal, non-bladder cancers) – sensitivity (malignant)	C66,C68	Byu9	Sensitivity outcome	D, Sens
5	Urinary Tract cancers from GP data (CPRD only) – sensitivity		Byu9, B837, B83z, B4A, B49	Sensitivity outcome	Sens
6	Urinary tract neoplasms of uncertain or unknown behaviour - sensitivity	D41	B917, B91z, BA04	Sensitivity outcome	Sens
Censoring variables					
7	Other non-UT cancers	C00-C99, D00-09 (excl. C64-68, D09.0, D09.1)	B (excl. Byu9, B837, B83z, B4A, B49, B49, B837, selected BB4 codes)	Censoring	
8	End of study period			Censoring	
9	End of GP practice coverage			Censoring	
10	Use of other SGLT-2 (since start of follow-up)			Censoring	
11	Use of fixed-dose combinations of			Censoring	

No.	Variable	ICD-10 / ICD-O-3 codes	READ codes	Outcome / Censoring variable	Analyses ¹
	SGLT-2 inhibitors with DPP-4 inhibitors				
12	Patient transfer			Censoring	
13	End stage renal disease / renal dialysis			Censoring	
14	All-cause mortality (excluding UT cancer mortality)			Censoring	
15	Discontinuation of primary exposure			Censoring for as-treated analysis	
16	UT cancer characteristics (based on staging, TNM codes, etc)			Sensitivity outcome / descriptive	D, Sens

1 D=Descriptive, P =Primary , S = secondary, F = further, Sens = sensitivity, NCC =Nested-case-control, MSM – marginal structural models

**ANNEX 6. COVARIATES TO BE CONSIDERED FOR INCLUSION IN
THE PROPENSITY SCORE MODEL.**

No.	Variable
Socio-demographic variables	
1	Age
2	Sex
3	Socioeconomic status
4	Calendar year of index date
5	Duration of look-back period
6	Duration of treated diabetes at index date
Diabetic complications	
7	Diabetic retinopathy or diabetic maculopathy
8	Diabetic nephropathy
9	Diabetic neuropathy
10	Peripheral vascular disease
11	Diabetic lower limb severe complications
Urinary tract related comorbidities	
12	Kidney or genitourinary stones
13	Prior history of UTI or pyelonephritis
14	Liver disease
15	eGFR
16	Renal impairment
17	Prior ICU admission
18	Pancreatitis

19	BMI (when available)
20	Smoking (when available)
21	Alcohol use (when available)
22	HbA1c (when available)
23	Albuminuria testing
Cardiovascular Diseases	
24	Congestive heart failure
25	Blood pressure measurements
26	Hypertension
27	Stroke
28	Myocardial infarction
29	Autoimmune disease
30	COPD
31	Time since first diabetes diagnosis
Other non-diabetes medications	
32	Antihypertensives/diuretics
33	Non-steroidal anti-inflammatory drugs (NSAIDs)
34	Oral steroids
35	Statins, fibrates
36	Lipid modifying agents
37	Zoledronic acid
38	Antibiotics
39	Other drugs

BMI=body mass index; COPD=chronic obstructive pulmonary disease; eGFR=estimated glomerular filtration rate; HbA1c=glycated haemoglobin A1c; HF=heart failure; ICU=intensive care unit; MSM=marginal structural model; NCC=nested case-control; PS=propensity score; UTI=urinary tract infection.

SIGNATURE

PRINCIPAL INVESTIGATOR SIGNATURE

Study Title: Post-authorisation safety study to assess the risk of urinary tract malignancies in relation to Empagliflozin exposure in patients with type 2 diabetes: a multi-database European study

Trial Number: 1245.97

Study protocol version: 8.0

I herewith certify that I agree to content of Study protocol version 8.0 and to all documents referenced in the study protocol version 8.0.

Date: 02-Jun-2023

Name: [REDACTED]

Signature: [REDACTED]

DocuSigned by:
[REDACTED]
Signer Name: [REDACTED]
Signing Reason: I approve this document
Signing Time: 02-Jun-2023 | 12:05:57 AM PDT
[REDACTED]

Affiliation: [REDACTED] Company

APPROVAL / SIGNATURE PAGE

[figure not shown]
[figure not shown]
[figure not shown]
[figure not shown]
[figure not shown]
[figure not shown]
Document Number: c03856813

Technical Version Number: 11.0

Document Name: 1245-0097-clinical-trial-protocol

Title: Post-authorisation safety study to assess the risk of urinary tract malignancies in relation to empagliflozin exposure in patients with type 2 diabetes: a multi-database European study

Signatures (obtained electronically)

Meaning of Signature	Signed by	Date Signed
Approval-EU Qualified Person Pharmacovigilance		15 Jun 2023 14:04 CEST
Verification-Paper Signature Completion		15 Jun 2023 14:13 CEST
Approval		15 Jun 2023 15:02 CEST
Approval-On behalf of [REDACTED] or VP or [REDACTED]		15 Jun 2023 15:21 CEST
Approval		15 Jun 2023 16:57 CEST
Approval-Team Member Drug Safety		19 Jun 2023 17:28 CEST

(Continued) Signatures (obtained electronically)

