8.3.4 Censoring of follow-up time

The following events lead to censoring: all-cause mortality, emigration, patient transfer, meeting specific exclusion criteria (see exclusion criteria in [Section 8.2.5](#)) and end of study period. Follow-up times will be censored at any of these events, whichever occurs first. In the primary AT analysis discontinuation of index drug treatment is an additional censoring variable. Treatment discontinuation is defined either by

- A switch from the index drug to any other drugs (empagliflozin, DPP-4 inhibitor, or other SGLT-2 inhibitor), or to a fixed-dose combination of a SGLT-2 inhibitor with a DPP-4 inhibitor (identified from the ATC class A10BD) plus a 3-month period following the switch, or
- As the stop date plus a 3-month period following it. The stop date is the end date of the first continuous exposure period of the index drug, where continuous treatment is defined as having consecutive prescriptions separated by 30 days or less ([Figure 1](#)).

The 3-month period after the switch or the stop date is used to allow for a delay in the diagnosis of cancer [[R16-2539](#)]. In a sensitivity analysis this time period is extended to 6 months.

Switch to a fixed-dose combination including the same index drug and drugs other than DPP-4 inhibitors and SGLT-2 inhibitors is not considered a censoring variable (for example, switch from sitagliptin to a fixed-dose combination including sitagliptin and pioglitazone).

[figure not shown]

Figure 1

Discontinuation of index drug due to stopping of index drug or switching of index drug. In the primary analysis follow-up is censored at treatment discontinuation.

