8.3.5 Follow-up time

For the primary AT analyses, the follow-up time (time at risk) will begin 6 months after the index date (lag period to account for empirical induction/promotion period of cancer) and end at urinary tract (bladder, renal or other) cancer or at any of the censoring events including discontinuation of index drug treatment.

For the sensitivity ITT analyses, the follow-up time will begin 6 months after the index date and end at urinary tract (bladder, renal or other) cancer or any of the censoring events excluding treatment discontinuation of index drug.

Patients with censored follow-up time will not be able to re-enter study cohort at a later time point. Follow-up will not be censored if oral or injectable glucose lowering drugs other than the index drugs are prescribed in addition to empagliflozin, a DPP-4 inhibitor, or a SGLT-2 inhibitor after the index date.

The lag period of 6 months is to account for an empirical induction/promotion period. Information in the first 6 months after the index date (i.e., first 6 months of follow-up) will be excluded, including patients with less than 6 months of follow-up and all occurrences of cancer within the first 6 months of follow-up, in order to consider a biologically meaningful induction/promotion time window. Sensitivity analyses will expand the lag period to 12 months.

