Emigration from the study country	Censoring of follow-up time occurs at the date of emigration from the study country. Applied in all analyses.	UK: CPRD-GOLD and Aurum Sweden: Total population register ¹ Finland: Population register centre
Patient transfer	Censoring of follow-up time occurs at the date of patient transfer. Applied in all analyses.	UK: CPRD-GOLD and Aurum Sweden: NA Finland: NA
Incidence of any cancer during follow-up	A registered diagnosis of any cancer (excluding non-melanoma skin cancer) during follow-up. (ICD-10, ICD-7, ICD-O-3 and READ diagnosis codes in Annex I) Applied in all analyses.	UK: CPRD-GOLD and Aurum Sweden: Swedish cancer registry (SCR) Finland: FCR
Diabetes diagnosis other than type 2	A diagnosis of type 1 diabetes or other non-type 2 diabetes during follow-up identified using the same algorithm as used for the exclusion criteria (Section 4.2.4) Relevant ICD-10 codes and READ diagnosis codes are provided in Annex I. Applied in all analyses.	UK: CPRD and Aurum Sweden: NDR, NPR Finland: reimbursement registry
End of study period	Censoring of follow-up time occurs at end of study date i.e. 31 December 2020 (2021 for UK-CPRD). Applied in all analyses.	NA

Proprietary confidential information © 2024 Boehringer Ingelheim International GmbH or one or more of its affiliated companies

Treatment discontinuation (AT exposure- main analysis)	Censoring of follow-up time occurs 90 days after 
 - last day of medication (i.e. stop date) - new prescription of the other study drug or of a SGLT-2 inhibitor Applied only in analyses using the AT exposure definition.	UK: CPRD-GOLD and Aurum Sweden: SPDR Finland: FPR
Treatment discontinuation (AT exposure- sensitivity analysis)	Censoring of follow-up time occurs 180 days after 
 - last day of medication (i.e. stop date) - new prescription of the other study drug or of a SGLT-2 inhibitor Applied only in the sensitivity analysis using the AT exposure definition.	UK: CPRD-GOLD and Aurum Sweden: SPDR Finland: FPR

¹ The National patient register will be used if data on immigration/emigration are unavailable from the Total population register.

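### Annex 5 row 7, as written, would censor UK patients on the plan's own uncertain-behaviour urinary tract codes, which its ICD column does not do

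*Protocol*

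**What the plan says.** Four rows of the table in Protocol Annex 5 matter here.

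- **Rows 1 to 3** define the primary outcomes. The UK codes are READ codes under B49, B4A, B837, B83z, Byu9 and selected BB4 codes.
- **Row 6** is labelled "Urinary tract neoplasms of uncertain or unknown behaviour - sensitivity". Its ICD-10 code is D41 and its READ codes are "B917, B91z, BA04".
- **Row 7** is the censoring variable for cancers outside the urinary tract. The ICD cell reads "C00-C99, D00-09 (excl. C64-68, D09.0, D09.1", closing the bracket there. The READ cell reads "B (excl. Byu9, B837, B83z, B4A, B49, B49, B837, selected BB4 codes".

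Protocol 8.3.4 states: "Follow-up times will be censored at any of these events, whichever occurs first". Protocol 8.3.5 adds: "Patients with censored follow-up time will not be able to re-enter study cohort at a later time point".

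SAP Table 4 (section 5.1.3) states the cancer censoring rule as "A registered diagnosis of any cancer (excluding non-melanoma skin cancer) during follow-up", applied in all analyses, with codes in SAP Annex I. That annex consists of separate files. The protocol's exclusion criterion on prior cancer (8.2.5) likewise spares non-melanoma skin cancer, and 8.3.4 censors patients who meet specific exclusion criteria during follow-up.

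On its own status, Annex 5 says: "The codes will be updated for the data applications".

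**The concern.** Row 7 is meant to stop follow-up at a cancer elsewhere in the body. Its READ cell does more than that. It takes every code beginning with B and subtracts a short urinary list, and that list leaves out the three codes that the row above calls urinary. A neoplasm that the plan itself places in the urinary tract, and does not call a confirmed cancer, would therefore censor a UK patient as a non-urinary cancer.

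At stake is UK case ascertainment for all three primary outcomes. UK outcomes come from CPRD records (8.3.2.1), and UK cancer registry data are not included (6.5), so no registry would recover a case lost this way. The UK estimate is then pooled with Swedish and Finnish estimates built on a different censoring rule.

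**Working it through.** **1. Code check**

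| Code in row 6 | In row 7's censoring range? | Spared by row 7? | Censors? |
|---|---|---|---|
| B917 (READ) | yes, begins with B | no | yes |
| B91z (READ) | yes, begins with B | no | yes |
| BA04 (READ) | yes, begins with B | no | yes |
| D41 (ICD-10) | no, outside C00-C99 and D00-D09 | not needed | no |

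None of the three READ codes falls under Byu9, B837, B83z, B4A, B49 or BB4. The two cells of row 7 disagree about the same group of neoplasms.

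**2. What follows if row 7 is programmed as written**

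- UK: B917, B91z or BA04, followed later by a B49 or B4A code. The first code censors (8.3.4), there is no re-entry (8.3.5), and the confirmed cancer is not counted.
- Sweden or Finland: D41, followed later by C67 or C64. D41 does not censor and the cancer is counted.
- In the UK, a row 6 record is at once the sensitivity outcome and a censoring code.

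**3. Skin cancer.** Neither cell of row 7 makes an exception for non-melanoma skin cancer. Protocol 8.2.5 and SAP Table 4 both do.

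**4. Cost in UK power if loss is equal in both arms**

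Inputs from the footnotes to Protocol Table 7: 16,360 UK empagliflozin initiators, 1:3 matching, 2.4 years, rates of 111.5, 66.7 and 26.5 per 100,000 person-years, and 5% alpha (taken as two-sided). The abstract gives 16,887 UK initiators; the footnote figure is used because the stated power rests on it.

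Events = 16,360 × 4 × 2.4 × rate. For urinary tract cancer this is 157,056 × 0.001115 = 175.1.

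Power (Schoenfeld) = Φ(√(events × 0.25 × 0.75) × ln HR − 1.96). At HR 1.5: √32.83 × 0.4055 − 1.96 = 0.363, so power is 64.2%.

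Reproduction at HR 1.5: 64.2%, 43.5% and 20.4%, against 63.7%, 43.1% and 20.3% in Table 7 (urinary tract, bladder, renal). At HR 2.0 the same form is within 2 points only for urinary tract cancer, so only HR 1.5 is used below.

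The share of UK cases with an earlier uncertain-behaviour code is not in the documents. Over an assumed range:

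| Assumed UK loss | Urinary tract events | Power, urinary tract | Power, bladder | Power, renal |
|---|---|---|---|---|
| 0% | 175.1 | 64.2% | 43.5% | 20.4% |
| 5% | 166.4 | 62.0% | 41.7% | 19.6% |
| 10% | 157.6 | 59.6% | 39.9% | 18.8% |
| 20% | 140.1 | 54.7% | 36.2% | 17.2% |
| 30% | 122.6 | 49.4% | 32.4% | 15.6% |

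**5. Effect on the HR if loss differs by arm**

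Observed HR ≈ true HR × (1 − loss on empagliflozin)/(1 − loss on DPP-4 inhibitors). With an assumed 20% and 10%: 1.50 × 0.80/0.90 = 1.33 and 1.00 × 0.80/0.90 = 0.89, in the UK only.

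Pooled, using inverse-variance weights with no between-country variance (information = events × allocation product):

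- UK: 175.1 × 0.1875 = 32.8
- Sweden: 32,334 × 2 × 2.2 × 0.001645 = 234.0 events; × 0.25 = 58.5
- Finland: 18,269 × 3 × 2.4 × 0.001615 = 212.4 events; × 2/9 = 47.2

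UK share = 32.8/138.5 = 0.237. Pooled HR = exp(ln 1.50 + 0.237 × ln(0.80/0.90)) = 1.46. With equal country weights it would be 1.44.

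**The case against.** The best defence is that Annex 5 is not the operative list. It announces its own revision, Protocol 8.3 leaves final operational definitions to the SEAP, and the SAP points to code files outside the released text. The wording of SAP Table 4, and row 7's own label, speak of cancers; neither would by itself take in a neoplasm of uncertain behaviour. The READ cell also carries no SNOMED codes, although SAP 5.2.1 uses them for Aurum, which supplies 8,545 of 16,887 expected UK empagliflozin initiators (Protocol Table 6). It looks like unfinished shorthand. On skin cancer, the protocol body and the SAP already agree.

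Much of this stands. It limits what can be claimed about the analysis, but it does not make row 7 right. Annex 5 is the only censoring code list visible in the two documents, and a general promise to update does not identify this conflict.

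A reader might infer more than the documents support:

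- **That UK events are being lost.** The SAP code files may already be correct. Nothing shows how often GPs record B917, B91z or BA04 before a confirmed cancer, and Nordic outcomes come from registries, where a provisional record may not arise at all.
- **That a count of lost events follows from the interim report.** The 164 urinary tract and 98 bladder events in Protocol 6.1.1 come from GOLD only and were observed. If row 7 had been applied, they are already net of any loss; if not, row 7 was not in force. Applying a loss percentage to them is unsound either way.
- **That the UK HR is biased towards safety.** The protocol raises more frequent urinary screening in empagliflozin users (8.1). More work-up could produce more provisional codes or quicker confirmation; the documents establish no direction.
- **That the lower UK bladder and renal rates reflect this mechanism.** Nothing ties them to it.
- **That the row 6 analysis necessarily fails in the UK.** The SAP tables defining further outcomes are not in the released text, so any rule for an outcome and a censoring code on the same date cannot be seen.

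**Conclusion.** Row 7 is wrong as written. Its READ cell conflicts with its own label, with row 6 and with its ICD cell, and neither cell matches Protocol 8.2.5 or SAP Table 4 on non-melanoma skin cancer. That rests on the text alone.

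The consequence is conditional. If the cell is programmed literally, UK patients coded with an uncertain-behaviour urinary neoplasm before a confirmed urinary tract cancer drop out as cases. The number of such patients is unknown. Equal loss in both arms would mainly cost UK precision: under an assumed 10% loss, about 5 points of UK urinary tract power at HR 1.5. Unequal loss would bias the UK HR, in either direction; under the assumed 20% versus 10% split a UK value of 1.50 becomes 1.33 and the pooled value about 1.46. The pooled result is therefore only modestly exposed even in that case. This is a correction to settle before analysis, not grounds to doubt the design.

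**What to change.** In Annex 5 row 7, do one of two things in the READ cell: add B917, B91z and BA04, with their SNOMED equivalents for Aurum, to the exclusions; or restrict the cell to malignant and in-situ non-urinary codes, as the ICD cell does. Exclude non-melanoma skin cancer in both columns. Confirm before analysis that SAP Annexes 1.1 to 1.3 follow the same rule. It would also help to report, by arm, how many UK patients have one of the three codes before a confirmed urinary tract cancer, since that count would replace the assumed shares used here.

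The cost is a code-list edit and a check of three existing files. No new data are needed.

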ANNEX IV LIST OF DRUG DOSAGES FOR EMPAGLIFLOZIN,	
DPP-4 INHIBITORS AND METFORMIN.....	185

LIST OF ABBREVIATIONS

Term	Definition / description
AT	As-treated analysis
ATC	Anatomical Therapeutic Chemical Classification System
AvoHILMO	Register of Primary Health Care Visits (Finland)
BI	Boehringer Ingelheim International GmbH
BMI	Body mass index
CI	Confidence interval
CLR	Conditional logistic regression
COPD	Chronic obstructive pulmonary disease
CPRD-GOLD	Clinical Practice Research Datalink, General practitioner OnLine Data (United Kingdom)
CPRD Aurum	Clinical Practice Research Datalink, Aurum (United Kingdom)
DPP-4	Dipeptidyl peptidase-4
eGFR	Estimated glomerular filtration rate
EMA	European Medicines Agency
ENCePP	European Network of Centres for Pharmacoepidemiology and Pharmacovigilance
EU	European Union
FCR	Finnish Cancer Registry
FDA	Food and Drug Administration
FPR	Finnish Prescription Register
GLP-1	Glucagon-like peptide-1
GP	General practitioner
GPP	Good Pharmacoepidemiology Practices
GPV	Good Pharmacovigilance Practices
HbA1c	Glycated hemoglobin A1c
HES	Hospital Episode Statistics (United Kingdom)
HF	Heart failure
HILMO	Care Register for Health Care (secondary care; Finland)
HR	Hazard ratio
ICD-10	International classification of diseases

Proprietary confidential information © 2024 Boehringer Ingelheim International GmbH or one or more of its affiliated companies

Term	Definition / description
IPTW	Inverse-probability of treatment weights
IR	Incidence rate
ITT	Intention-to-treat analysis
LISA	Longitudinal integration database for health insurance and labour market studies
MDRD	Modification of Diet in Renal Disease study
MI	Myocardial infarction
MSM	Marginal structural model
NCC	Nested case-control
NDR	National diabetes register (Sweden)
NHS	National Health Service
NICE	National Institute for Health and Care Excellence
NPR	National patient register (Sweden)
NSAID	Non-steroidal anti-inflammatory drugs
ONS	Office for National Statistics
PASS	Post-safety study
PH	Proportional hazards
PID	Personal identification number
PRAC	Pharmacovigilance Risk Assessment Committee
PS	Propensity score
PSUR	Periodic Safety Update Report
PY	Person-years
RMP	Risk management plan
RR	Relative risk
SCR	Swedish cancer registry
SEAP	Statistical/Epidemiological Analysis Plan
SF	Statistics Finland
SGLT-2	Sodium glucose co-transporter-2
SID	Study identification number
SII	Social Insurance Institution (SII)
SIR	Standardized incidence ratio

1. INTRODUCTION

This statistical analysis plan refers to the final version of the pharmacoepidemiological study protocol entitled “Post-authorisation safety study to assess the risk of urinary tract malignancies in relation to empagliflozin exposure in patients with type 2 diabetes: a multi-database European study”, version 6.0 dated February 10th, 2022 unless otherwise stated.

This is an observational, comparative cohort safety study based on European healthcare databases and includes databases from the UK, Sweden and Finland.

The study will use a new user design to compare new users of empagliflozin to new users of DPP-4 inhibitors in order to assess the risk of urinary tract malignancies.

Individuals with similar treatment and clinical history will be matched by deriving propensity scores conditional on factors potentially affecting the treatment and outcome.

In the primary analysis, propensity-score (PS) matched cohorts will be derived from the study base by matching patients who initiate empagliflozin with patients who initiate DPP-4 inhibitors at index date with a variable matching ratio of up to 1:3 (1:1 matching in a sensitivity analysis) using greedy matching methods.

In addition, patients using metformin in free or fixed dose combination with empagliflozin or with a DPP-4 inhibitor will be identified and the primary analysis will be repeated within this subset of patients.

Proprietary confidential information © 2024 Boehringer Ingelheim International GmbH or one or more of its affiliated companies

2. RESEARCH QUESTION AND OBJECTIVES

2.1. RESEARCH QUESTION

The aim of the study is to assess the risk of urinary tract malignancies in patients initiating empagliflozin compared to patients initiating a DPP-4 inhibitor.

[figure not shown]
2.2. OBJECTIVES

Primary objectives

- i. To estimate the adjusted hazard ratio and incidence rates of all urinary tract cancers (bladder, renal and other urinary tract cancers) in patients initiating empagliflozin compared to patients initiating a DPP-4 inhibitor.
- ii. To estimate the adjusted hazard ratios and incidence rates of bladder cancer in patients initiating empagliflozin compared to patients initiating a DPP-4 inhibitor.
- iii. To estimate the adjusted hazard ratios and incidence rates of renal cancer in patients initiating empagliflozin compared to patients initiating a DPP-4 inhibitor.

Secondary objectives

- i. To estimate the adjusted hazard ratio and incidence rates of each primary outcome (all urinary tract cancers, bladder cancer, renal cancer) with respect to:
 - a. Increasing cumulative dosage to empagliflozin.
 - b. Dosage of empagliflozin prescribed per use (10mg vs. 25mg).
 - c. Time since first prescribed/dispensed dose of empagliflozin.

Proprietary confidential information © 2024 Boehringer Ingelheim International GmbH or one or more of its affiliated companies

